5.2.2 Secondary and Exploratory Outcome Variables (if applicable)

We will examine the effect of the technology- and telephone-intervention on daily cigarette, e-cigarette, and smokeless tobacco use; nicotine dependence (Fagerström Test of Nicotine Dependence16 [FTND]) and PTSD symptom levels (PTSD Checklist-517 [PCL-5]) at Weeks

8, 12, and 24; and bioverified seven- and 30-day point prevalence abstinence at Weeks 12 and 24.

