6.4.1 Statistical Design

Data analytic plan: Prior to analysis all data will be examined for anomalous and missing values and described in detail. The description of the data is a key aspect of this work as it

informs future studies. Qualitative data (Focus groups and Aim 1) will undergo thematic analysis using a hybrid qualitative methodology incorporating deductive and inductive approaches. For the preliminary codebook for interviews, we will start with deductive codes (based on the interview guide and prior literature). Iteratively, we will add inductive codes (using grounded theory methodologies⁸⁹⁻⁹¹). We will apply codes (phrases that explicitly describe segments of data) to relevant quotations for data sorting. Once a preliminary codebook has been created, a minimum of two coders will assist with coding and will apply initial codes as well as develop new codes following review of each additional transcript. All coders will document the process of creating new codes and any changes in previously determined codes. We will hold weekly meetings with coders to aid in calibration of coding and review and discuss discrepancies if necessary. We will calculate inter-rater reliability (Cohen's k for codes) and will resolve discrepancies to ensure consistent code application across raters and over time (.80 or above will be considered acceptable). We will identify themes (recurring and unifying concepts) during iterative thematic analyses until saturation is reached. 90,92 ATLAS.ti software will be used to organize the unstructured interviews objectively. Quantitative Data: To evaluate feasibility (Aim 1) we will calculate the: a) proportion of those eligible among those screened; b) proportion enrolled among those eligible (goal ≥ 50%); c) the rate of enrollment (goal four participants per month); e) adherence to NRT in those prescribed NRT, defined as total days taking NRT divided by total days prescribed NRT (goal ≥ 70% adherence in intervention condition); e) study completion rate in both conditions. We will also examine iCO and SQC app usage patterns (number of days each app is used per participant self-report and total data used by each app over the study period) in intervention condition participants and examine the relationship between app usage and study outcomes. To assess acceptability (Aim 1) we will calculate the percentage of participants in the intervention condition who rate each of the technology components as moderately acceptable or higher as measured by the SUS^{72,73} and the selfreport questionnaire assessing acceptability of the telephone manual (objective: ≥ 75% participants rate SUS ≥ 70 for iCO and SQC and rate telephone sessions as "moderate" or higher acceptability). Qualitative data will be combined with the quantitative acceptability data in a mixed methods analysis for cross-validation of the techniques. Failure to meet the feasibility and acceptability objectives will drive a major revision of the study protocol for future studies. We will also compare retention rates of the two treatment conditions (proportion of participants in each condition that engages in four or more sessions) (Aim 2 Hypothesis) and in seven- and 30-day point-prevalence smoking abstinence rates. FTND scores, and PCL scores (Exploratory Hypotheses) at Weeks 8, 12, and 24. The randomization procedure should result in covariate effects being distributed equally between the treatment conditions. If, however, the preliminary analyses indicate the treatment conditions vary on potentially confounding variables such as age or number of previous quit attempts, these covariates will be included in a multivariate model. Comparing treatment conditions that include time as a factor, the prototypical model will be a nonlinear mixedeffects model for dichotomous outcomes. Given the limited number of assessment points, the most parsimonious model will be a general linear model for each outcome. Planned contrasts among the intervention condition will directly test each hypothesis. Quantitative

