6.4.3.4 Analysis of Subject Characteristics

Means or proportions of participants will be compared across the various categories of VA facilities by age, race/ethnicity, gender, level of education, employment, military branch and era, and marital status. Prior to testing the study hypotheses, the distributions of all variables will be examined to ensure that they have adequate range and variance and meet all necessary assumptions of the statistical methods to be used. Cronbach's alpha will serve as the index of internal reliability for this step. Primary analyses will be performed by intent to treat. All patients who are assigned a treatment condition will be considered enrolled.

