6.4.5 Handling of Missing Data

Missing data can arise from several sources, including participant dropout or participant failure to complete occasional measures. For the analyses of smoking outcomes, we will conduct analyses in two ways: a complete-case approach using observed data, and to assume missing as the negative outcome (e.g., missing=non-abstinent) to obtain a range of the intervention effects. We will use the maximum likelihood approach of the mixed model to accommodate missing outcome variables without bias under the assumption of missing at random, meaning that missingness is random conditional on observed variables. This is a reasonable assumption for missing data not under the participants' control and sporadic missing items on measures.

7 - Trial Administration

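### For FTND and PCL-5, section 6.4.1 names only a general linear model, while section 6.4.5 relies on a mixed-model likelihood for its missing-at-random claim; the two need reconciling

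*Combined protocol and SAP*

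**What the plan says.** Section 6.4.1 (Statistical Design) lists among its comparisons "FTND scores, and PCL scores (Exploratory Hypotheses) at Weeks 8, 12, and 24". It then gives two model statements in succession. For comparisons with time as a factor, "the prototypical model will be a nonlinear mixedeffects model for dichotomous outcomes". The next sentence, citing how few assessments there are, says that "the most parsimonious model will be a general linear model for each outcome". No mixed model for a continuous outcome appears there or elsewhere. The software is SPSS; no procedure is named.

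Section 6.4.5 (Handling of Missing Data) first sets two analyses for smoking outcomes, complete case and missing counted as the negative outcome. It then says: "We will use the maximum likelihood approach of the mixed model to accommodate missing outcome variables without bias", under missing at random.

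FTND and PCL-5 are both measured at Weeks 0, 8, 12 and 24 (sections 6.1.3 and 6.2). Section 6.4.2 bases its power statement on at least 60 completers of the 80 randomised.

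**The concern.** The missing-data claim belongs to a model that the plan does not specify for these two scores. A likelihood-based repeated-measures model lets a participant's Week 0 and Week 8 scores inform the estimate at Weeks 12 and 24 when later scores are absent. An ordinary general linear model does not. Fitted to all visits together, it keeps only complete records. Fitted visit by visit, it keeps only those seen at that visit, and earlier follow-up scores play no part.

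Missing scores are a realistic prospect. The background section describes high dropout among young veterans with PTSD, and section 6.3.7 provides for withdrawal when symptoms worsen, so missingness may be linked to the scores themselves. Section 6.4.2 gives estimation of effect sizes for a later trial as a purpose of this pilot, so a distorted FTND or PCL-5 difference could be carried into that design. Leaving the model open also lets it be chosen after the data are seen.

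**Working it through.** **1. The plan's own figure.** Section 6.4.2 says 60 completers give adequate power for large effects, without alpha, sidedness, power or a numerical effect. Assuming two-sided alpha 0.05, a large effect of d = 0.8 and 30 per arm, the noncentral t gives 86.1% power. The statement is plausible, but it is built on completers. The detectable difference at 80% power (normal approximation) is (1.960 + 0.842) × √(2/n): 0.72 SD for n = 30 and 0.63 SD for n = 40 per arm. The second figure is a ceiling on what a likelihood analysis could recover, since it regains only part of the lost information.

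**2. Who is left out under a general linear model.** The plan does not say whether there is one model over all visits or one per visit. Assume each of three follow-ups is missed independently with probability m:

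| m | all-visits model, 80 × (1 − m)³ | per-visit model, 80 × (1 − m) |
|---|---|---|
| 10% | 58 | 72 |
| 15% | 49 | 68 |
| 20% | 41 | 64 |

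At exactly 60 completers, an all-visits model omits 80 − 60 = 20 participants (25%).

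**3. Whether it biases the result.** This was checked by simulation. Common settings: 40 per arm, SD 1, equal correlation between visits, higher score worse, difference = intervention minus control at Week 24.

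First pattern: no true effect, 25% dropout after Week 8, random in controls, more likely with a worse Week 8 score in the intervention arm (logistic slope 1 per SD), correlation 0.5 to 0.7.

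- Unadjusted completers: bias about −0.11 to −0.15 SD, false-positive rate 7-9%.
- Per-visit model adjusted for Week 0: bias about −0.05 SD, false-positive rate about 6%.
- Maximum likelihood: bias about 0.

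Other patterns: correlation 0.6, dropout at Weeks 12 and 24 depending on the last observed score, about 57-61 completers, 1,500 runs each. Entries are the mean estimated difference, with the SD of the estimate in brackets.

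| dropout pattern | true difference | completers | likelihood |
|---|---|---|---|
| unrelated to score | 0 | 0.01 (0.257) | 0.01 (0.242) |
| score-related alike in both arms | 0 | −0.01 (0.268) | −0.01 (0.259) |
| score-related in controls only | 0 | 0.16 (0.253) | 0.01 (0.239) |
| opposite by arm | 0 | 0.32 (0.258) | 0.00 (0.256) |
| score-related in controls only | −0.80 | −0.64 (0.262) | −0.80 (0.250) |

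**4. Reading the results.** Bias appears only when dropout depends on score differently in the two arms. In the first two rows there is none, and likelihood gains little precision. In the first pattern, the completer bias is roughly half the sampling SD of about 0.25 (0.11/0.25 = 0.44; 0.15/0.25 = 0.60). Adjusting for Week 0 reduces it to 0.05/0.25 = 0.20 without removing it.

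**The case against.** The best defence is that 6.4.5 shows the intention. It commits firmly to mixed-model likelihood, whereas the sentence in 6.4.1 only calls a general linear model the most parsimonious. A linear model with correlated errors fitted by likelihood may also be called a general linear model, and it would keep incomplete records. This stands to a degree: the final model is unclear, rather than plainly wrong. But a plan that can be read either way does not deliver the property that 6.4.5 asserts.

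Three stronger readings are tempting, and the documents do not support them.

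- *That a quarter of the sample will be lost.* Sixty completers is a floor for power, not a forecast. Section 6.1.3 invites people who stop treatment to complete follow-up, and the loss of 20 applies only to an all-visits model at that floor.
- *That intent to treat is breached.* The commitment is "Primary analyses will be performed by intent to treat". FTND and PCL-5 are listed under exploratory hypotheses, so that sentence does not cover them.
- *That daily tobacco use shares the fault.* Section 5.2.2 names "daily cigarette, e-cigarette, and smokeless tobacco use; nicotine dependence" as outcomes, but 6.4.1 does not list daily use among its comparisons. If it counts as a smoking outcome, 6.4.5 openly states: "For the analyses of smoking outcomes, we will conduct analyses in two ways: a complete-case approach using observed data". Dropping cases would then be declared policy, and a Gaussian model suits such counts poorly.

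The asymmetric dropout in the simulation is also assumed. Nothing in the documents shows that reasons for dropout will differ by arm.

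**Conclusion.** The point holds for FTND and PCL-5. Section 6.4.5 claims a missing-data property that the only model named for these scores in 6.4.1 does not have when fitted as an ordinary general linear model. The consequence is conditional: about 0.11-0.15 SD of bias at Week 24 for unadjusted completers and about 0.05 SD for a baseline-adjusted per-visit model if dropout is score-related in one arm only, and none if dropout is random or alike in both arms. The sizes rest on assumed correlation (0.5-0.7), about 25% dropout and an assumed strength of dependence, and are illustrative; opposite dropout patterns by arm gave 0.32 SD.

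Likelihood protects only under missing at random. Section 6.4.5 itself defends that assumption for losses outside participants' control and for occasional missing items, so dropout because of worsening remains a limitation under any of these models.

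The outcomes are exploratory, and neither the Aim 1 feasibility and acceptability results nor the Aim 2 retention comparison depends on this. The change is worth making because it is cheap and removes a post hoc choice of model.

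**What to change.** In 6.4.1, replace the general-linear-model sentence, as far as it concerns FTND and PCL-5, with one linear mixed model for repeated measures per outcome. Specify:

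- fixed effects for arm, visit and arm-by-visit, with the Week 0 score included;
- whether Week 0 enters as a response or as a covariate, because as a covariate a participant with no follow-up score contributes nothing;
- unstructured covariance across visits, with a named simpler structure if the model does not converge;
- restricted maximum likelihood, fitted in SPSS MIXED to all randomised participants with available data;
- the arm difference with its confidence interval at Weeks 8, 12 and 24.

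Keep the general linear model as a sensitivity analysis, stating whether it is per visit or over all visits and whether it adjusts for Week 0. In 6.4.5, tie the likelihood statement to the FTND and PCL-5 models by name.

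The cost is a few sentences of SAP text and a few more covariance parameters to estimate from 80 participants. No new data or software are needed.

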6.4.2 Sample Size Considerations

Power Analysis: The primary aim of this pilot study is to gather relevant information including preliminary outcomes, to evaluate feasibility and acceptability for the purpose of refining our intervention and to provide empirical data for recruitment, attrition and effect size estimation for a future RCT. Therefore, the sample size of n=80 was determined primarily by practical and clinical reasons and not driven by estimated effect sizes. We do plan to evaluate the key outcomes, however, so we estimated the minimally detectable effect sizes for those tests. Results indicate that a total sample of at least 60 completers with planned contrasts as described in the Analysis section should provide adequate power to detect large effect sizes.

6.4.3.4 Analysis of Subject Characteristics

Means or proportions of participants will be compared across the various categories of VA facilities by age, race/ethnicity, gender, level of education, employment, military branch and era, and marital status. Prior to testing the study hypotheses, the distributions of all variables will be examined to ensure that they have adequate range and variance and meet all necessary assumptions of the statistical methods to be used. Cronbach's alpha will serve as the index of internal reliability for this step. Primary analyses will be performed by intent to treat. All patients who are assigned a treatment condition will be considered enrolled.

6.4.5 Handling of Missing Data

Missing data can arise from several sources, including participant dropout or participant failure to complete occasional measures. For the analyses of smoking outcomes, we will conduct analyses in two ways: a complete-case approach using observed data, and to assume missing as the negative outcome (e.g., missing=non-abstinent) to obtain a range of the intervention effects. We will use the maximum likelihood approach of the mixed model to accommodate missing outcome variables without bias under the assumption of missing at random, meaning that missingness is random conditional on observed variables. This is a reasonable assumption for missing data not under the participants' control and sporadic missing items on measures.

7 - Trial Administration

7.1 Ethical Considerations

- 1) Risk of Distress or Embarrassment: To protect against risks of distress or embarrassment, researchers will inform participants that participation is voluntary. They will be informed that they may choose to not respond to any question asked at any point in the study, may stop a session at any time, or end their participation in the study at any time. The PI and other study team members have substantial experience and expertise in these issues from work in prior research studies. To minimize risk of distress associated with completion of self-report forms, we have chosen self-report assessments that are unlikely to lead to participant distress. Acceptability questionnaires administered during the CAP are at very low risk of contributing to clinically significant distress.
- 2) Exacerbation of PTSD symptoms: This risk will be minimized by providing participants in both conditions with support and behavioral intervention designed to facilitate smoking cessation with a minimal amount of stress. All participants will be able to continue or seek any mental health treatment at any point in the study. Referrals for psychotherapy and/ or emergency behavioral health services will be made when deemed necessary.
- 3) Nicotine withdrawal symptoms (RCT only): To minimize withdrawal symptoms, both conditions will receive treatment; there is no placebo condition in this trial. All participants will be offered NRT and will be counseled about the symptoms of nicotine withdrawal and coping strategies.
- 4) Use of NRT (RCT only): To minimize risks of adverse effects of NRT, the risks, benefits and alternatives of these medications will be discussed in detail by [name], PI, in the office visit at Week 0 prior to randomization in all participants. Each participant's medical and medication history will be reviewed in detail and prescribing practices will follow VA prescribing guidelines, which includes assessment of nicotine dependence level, assessment of safety and risks and benefits for the participant, review of medical record and medication history, and participant preference. Prior to initiation of the medication trial, verbal informed consent will be obtained from participants at this face-to-face visit. Participants will be provided with a wallet card with the study psychiatrist's contact information and will be encouraged to contact her with any side effects or other concerns related to prescribed medications. Following the initial visit, a study psychiatrist, blinded to group assignment, will contact participants in both conditions monthly by phone to monitor for side effects, adjust dosing or discontinue medication, and renew refills as needed. The potential risks of different formulations of NRT are summarized below.

Risks of Any NRT:

- Cardiovascular risk: Participants with history of heart attack or stroke will require medical clearance from a VA primary care physician prior to receiving NRT during the study.
- Risk of overdose: To minimize risk of overdose, [name] and the study psychiatrist to be named will adhere to VA prescriber dosing guidelines. Participants will be advised not to smoke while using NRT products. Participants will be advised that if these symptoms occur,

they should stop using NRT and will be told to contact the study team and/ or seek emergency care immediately, depending on severity of symptoms.

- Pregnancy: Due to the unknown risks of NRT in pregnancy, participants who are pregnant will be excluded at screening (self-report of pregnancy and/ or urine pregnancy test). Women of childbearing age will be advised to either avoid NRT or use an effective form of contraception if they accept NRT therapy during the study.
- Poisoning: Parents of small children should store NRT out of reach of children to prevent a child from consuming them and being poisoned.
- Potential drug-drug interactions or difficulty metabolizing NRT: The PI will review the medical history in the medical record, medication list including over the counter and herbal supplements, and will perform a thorough clinical assessment at the medication management visit to minimize risk of drug-drug interactions. Should side effects occur, the study psychiatrist will adjust or discontinue the medication.

Risks of specific formulations of NRT:

- Skin irritation (patch) may be relieved by the use of 1% hydrocortisone or Eucerin cream available over-the-counter, and avoiding reapplication of the patch to the same site.
- Insomnia (patch) may be managed by removal of the patch at night during sleep.
- Irritation in the mouth or jaw (gum or lozenge) can be managed by adjusting and/ or discontinuing the medication by the study psychiatrist.
- Other nonspecific side effects (diarrhea, an upset stomach, muscle aches, increased blood pressure) can be managed through dose reduction or adjustment, switch to alternative form of NRT, or discontinuation of NRT, depending on clinical presentation and evaluation of the PI.

Monitoring to ensure safety: Participants will be monitored in the following ways:

- At the screening visit, they will undergo a diagnostic interview and will be assessed for psychiatric acuity to ensure that participation is safe and participants are sufficiently stable to participate.
- Review of the VA electronic medical record, collection of medical and psychiatric history, and psychiatric diagnostic interview will be conducted at screening to ensure safety of participation.
- Medication management evaluation will be conducted prior to randomization at Week 0 to evaluate the safety, risks, and benefits of NRT in each participant per VA prescribing guidelines.
- Study psychiatrist blinded to group assignment will contact participants by telephone in both conditions once monthly to monitor NRT throughout the 24week study period.
- Participants will be provided with emergency contact information for the study team, study psychiatrist, and PI as well as the VA Suicide Prevention Hotline and those of nearest VA facilities and counselled to call or present for emergency care as needed.

Provision of emergency medical or psychiatric care: Participant safety will be a paramount concern during this research project. Participants will include veterans who are eligible for VA health care, including emergency or urgent care. Should any adverse events, medical or mental health emergencies occur during the course of the study, participants may seek emergency or urgent care at SFVAMC or their nearest emergency room. If a participant is injured as a result of being in this study, VA will ensure that treatment is made available at a VA medical facility. The costs of such treatment will be covered by the Department of Veterans Affairs. The Department of Veterans Affairs does not normally provide any other form of compensation for injury. Participants will be provided with the contact information for VA Regional Counsel in case they have any questions. Finally, we have identified a Medical Monitor, [name] M.D., who will oversee all aspects of safety monitoring throughout the study, and will assemble a Data and Safety Monitoring Board (DSMB) consisting of three experienced clinician-researchers: [name], Psychiatrist, SFVA/ UCSF; [name] M.D., Psychiatrist, UCSF; and [name] M.D, Internal Medicine physician, SFVA/ UCSF.

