6.1.1 Description of Intervention

The original treatment manual includes eight weekly sessions focusing on tobacco use and PTSD psychoeducation, behavioral coaching tailored for smokers with PTSD, scheduling a quit date in Session 5, and providing skills for relapse prevention. PTSD-specific skills include: controlled breathing, coping plans to manage trauma-related triggers, and strategies to manage anxiety sensitivity, emotional numbing, and low mood (see Figure 4). Consistent with the office-based manual, sessions will occur weekly, with identical duration to the original IC protocol (20-30 minutes per session), and will include use of a modified workbook tailored to the manual. Telephone sessions will be scheduled weekly and phone calls will occur proactively (therapist calls participant). The content of the revised manual and workbook will be thematically similar in approach, topic areas, and content to the officebased manual, but will be revised to include: (1) an interactive question-and-answer format aimed at engaging the participant more actively during telephone sessions; (2) prompts instructing participants to access the workbook at the beginning and end of sessions to minimize interruptions; and (3) prompts directing the participant to utilize the SQC app and iCO Smokerlyzer. SQC app will be populated with personalized information such as reasons for quitting, a coping plan for managing PTSD and smoking triggers, and a medication plan. The iCO Smokerlyzer enables participants to test their breath CO level anywhere and download the readings to their smartphones for review during telephone counseling sessions.

Session	Week	Core Content of Eight Intervention Sessions
1	1	Assess nicotine dependence, identify reasons for quitting, encourage med adherence if prescribed meds; introduce behavioral plan to reduce cigarette use; reinforce SQC app and iCO use
2	2	Set quit date, identify smoking triggers and PTSD symptoms related to smoking; introduce controlled breathing and coping plans for triggers and PTSD symptoms; reinforce SQC app and iCO use
3	3	Review assignment to practice coping with smoking triggers and PTSD symptoms, develop action plan to manage triggers and

		symptoms, assess adherence with medications; reinforce SQC app and iCO use
4	4	Implement behavior changes to prepare for quit date while managing PTSD symptoms; reinforce SQC, iCO use

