6.1.3 Selection of Instruments/Outcome Measures

Aim 1: Feasibility and Acceptability of the Intervention

- · Feasibility: We will calculate the: a) proportion of those eligible among those screened in rural and urban areas; b) proportion enrolled among those eligible; c) the rate of enrollment; d) adherence to medications (percentage of days participant takes NRT of total days prescribed); e) total number of sessions completed in each condition; f) iCO and SQC app usage data (intervention participants only); and g) study completion rate. To assess NRT adherence and estimate app usage data, participants will be asked to record daily medication adherence in a paper log using the TLFB method with specific anchor dates in a calendar, which will be mailed to the study team at each assessment time point. Pharmacy refill data will be reviewed at each time point to confirm TLFB self-report of medication adherence.
- · Qualitative Interview (Acceptability): We will conduct a 20-minute semi-structured, audiorecorded telephone interview at Week 8 with intervention condition participants only to

collect in-depth feedback about user satisfaction with features of the overall intervention and its components (telephone sessions, SQC app, iCO monitor). We will use a framework of open-ended questions based on an interview guide developed by the study team, similar to that used in the focus groups with the CAP (see 3B.4), but with a greater emphasis on the acceptability of the intervention and its individual components (telephone sessions, SQC app, iCO monitor) in a therapeutic context during a quit attempt. We will inquire about individual features of each component of the intervention and perceived helpfulness; feasibility and acceptability in rural and urban settings; acceptability of the intervention in a military/ veteran cultural context; anticipated barriers and facilitators of implementation; the balance of adequate therapeutic intervention versus time burden; scheduling; cost-effectiveness; and issues of mobile device accessibility and connectivity. Audio-recordings of the interviews will be transcribed and relevant portions about acceptability of the intervention will be noted.

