6.3.4 Recruitment, Enrollment and Retention6.3.5 On Study VisitsMEDICATION MANAGEMENT

Initial visit: The PI will meet with each participant at baseline (Week 0) prior to randomization to prescribe NRT (patch, gum, and/or lozenge) if desired, following a VA prescribing algorithm consistent with current prescribing guidelines.12,79 The session will be either in-person or through the telemedicine (V-tel) clinical services at the SFVAMC CBOCs. NRT will follow standard VA prescribing guidelines and will be based on (1) safety, (2) nicotine dependence level, and (3) participant preference. All participants will be instructed to set a goal of stopping cigarette, e-cigarette, and smokeless tobacco use during the course of study.

NRT monitoring: Following the initial visit, a study psychiatrist who is blinded to group assignment will contact participants in both conditions once monthly by phone to monitor for NRT side effects, adjust dosing, and renew refills. Participants who decline NRT will also receive a brief monthly check-in call to eliminate any potential therapeutic effect of these calls on study outcomes. All participants will remain on NRT as long as is clinically indicated throughout the 24-week study period, as determined by the study psychiatrist. Participants may contact the psychiatrist with any side effects or concerns related to NRT.

STUDY INTERVENTION PERIOD

Intervention condition: Details on the weekly telephone counseling sessions are provided in Section 6.1.4. Study therapists will conduct the sessions from private offices at SFVAMC, and veterans will participate via phone from their home or other location that is convenient for the.

Control condition: Details on the QL control condition are also provided in Section 6.1.4. QL sessions are also conducted via phone, and veterans will participate, as frequently as desired, from their home or other location that is convenient for the.

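### A participant who smokes until the Week 5 quit date cannot follow all the NRT instructions, and heeding the no-smoking advice can be scored as non-adherence against the 70% goal

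*Combined protocol and SAP*

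**What the plan says.** All references are to the combined protocol and SAP.

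- **Prescribing.** Section 6.3.5 (Medication Management): "The PI will meet with each participant at baseline (Week 0) prior to randomization to prescribe NRT", for those who want it. NRT may continue, as clinically indicated, over the 24-week study. A psychiatrist telephones monthly and can adjust doses and renew refills; section 7.1 adds discontinuation.
- **Sessions before quit week.** The section 6.1.1 table gives for Session 1 (Week 1): "encourage med adherence if prescribed meds; introduce behavioral plan to reduce cigarette use". Session 3 (Week 3) includes: "assess adherence with medications".
- **Quit date.** The same table marks Session 5, Week 5, as quit week, and section 6.1.4 also places the quit attempt in Week 5.
- **Smoking while on NRT.** Section 7.1: "Participants will be advised not to smoke while using NRT products". Section 3.3.2 gives the same instruction and ties it to a possible increase in heart attack or stroke.
- **Adherence measure.** Section 6.1.3: "percentage of days participant takes NRT of total days prescribed". Section 6.4.1 repeats the ratio and adds the target: "total days taking NRT divided by total days prescribed NRT (goal ≥ 70% adherence in intervention condition". Section 5.2.1 lists medication adherence among the primary feasibility variables.
- **Consequence.** Section 6.4.1 says that missing the feasibility and acceptability objectives leads to a major protocol revision for future studies.

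No section says on which day prescribed days begin, over which period the 70% is judged, or whether it applies to each person or to the arm mean.

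**The concern.** Before Week 5 the session plan assumes that participants still smoke, though less. In those weeks they hold a prescription, are encouraged to take it, and are told not to smoke while taking it. A participant who goes on smoking must set aside either the adherence message or the safety advice.

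The adherence ratio does not separate these cases. If prescribed days run from Week 0, a day without NRT because the participant smoked and heeded the advice looks the same as a day on which NRT was forgotten or refused. A shortfall against 70% could then reflect the conflicting instructions and say little about whether participants will use NRT. Because the result is meant to inform the design of later studies, the pilot could draw the wrong lesson from it. Separately from the statistics, participants should not receive instructions that conflict on a point to which the protocol itself attaches a cardiovascular risk.

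**Working it through.** The 70% is a target given without derivation, so there is no plan figure to reproduce. The check asks what adherence is possible for a participant who obeys the no-smoking advice.

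**Inputs from the protocol**
- Adherence = days taking NRT / days prescribed; goal at least 0.70 (6.1.3, 6.4.1).
- Prescribing visit at Week 0 (6.3.5); quit week is Week 5 (6.1.1, 6.1.4).
- NRT logs are returned at the assessments (6.1.3). Follow-up assessments are at Weeks 8, 12 and 24, so the candidate windows are T = 56, 84 and 168 days.

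**Assumptions, not stated in the protocol**
- Prescribed days start at Week 0, and Week 1 begins at prescription.
- The participant smokes until quit week and takes no NRT on smoking days.
- Prescribed days lost, d, run from 28 (quit on the first day of Week 5) to 35 (quit at the end of Week 5).

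**Ceiling = (T − d)/T**

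| Window | d = 28 | d = 35 |
|---|---|---|
| 8 weeks | 28/56 = 50.0% | 21/56 = 37.5% |
| 12 weeks | 56/84 = 66.7% | 49/84 = 58.3% |
| 24 weeks | 140/168 = 83.3% | 133/168 = 79.2% |

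**Post-quit use needed over 24 weeks.** 0.70 × 168 = 117.6 days. This is 117.6/140 = 84% of post-quit days with d = 28, and 117.6/133 = 88% with d = 35.

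**Shortest window in which 70% is possible, T = d/0.30.** 28/0.30 = 93.3 days (13.3 weeks); 35/0.30 = 116.7 days (16.7 weeks).

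**Relaxing the assumptions one at a time**
- *Prescribed days start at the quit date.* The pre-quit days leave the denominator and the ceiling is 100% in every window.
- *The participant stops smoking early.* The largest d compatible with 70% is 0.30 × T: 16.8 days over 8 weeks (16 whole days) and 25.2 over 12 weeks (25 whole days). Both fall before Week 5.
- *The goal is an arm mean.* If a share f reaches 100% and the rest sit at the ceiling c, then f = (0.70 − c)/(1 − c).
  - 8 weeks: (0.70 − 0.50)/0.50 = 40%, to (0.70 − 0.375)/0.625 = 52%.
  - 12 weeks: (0.70 − 0.667)/0.333 = 10%, to (0.70 − 0.583)/0.417 = 28%.

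**The case against.** A reader might infer that nobody who follows the instructions can meet the 70% goal over 8 or 12 weeks. The documents do not support that, for four reasons, all of which stand.

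1. Section 6.3.5 dates the prescribing visit. It does not say that prescribed days start then. The start rule may lie in the VA prescribing algorithm it cites, which is not reproduced. Session 5's task of coordinating with the prescriber is compatible with a later start.
2. No section ties the goal to Week 8 or Week 12. The only NRT period stated is the 24-week study, and there 70% is reachable even in the unfavourable scenario.
3. Nothing forbids stopping before Week 5. Section 6.3.5 asks only for a goal of stopping during the study, and early stoppers can reach 70%.
4. The goal may be an arm mean, which a minority of early stoppers could carry over 12 weeks.

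The reach is also limited. NRT is optional, the goal covers only those prescribed it, the stated consequence concerns future studies, and the Aim 2 retention comparison does not use it.

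The objection does not remove the conflict. Encouraging adherence in Week 1 and assessing it in Week 3 both suggest that NRT use is expected before quit week, and no passage squares this with the no-smoking advice. A quit-date start would not fully settle it either: Session 8 resets the quit date for those not abstinent, so a participant who lapses and then withholds NRT as advised could still lose adherence days.

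**Conclusion.** The point holds as a contradiction between instructions that carries into an undefined adherence denominator. A participant who smokes until quit week cannot comply with sections 3.3.2, 6.1.1, 6.3.5 and 7.1 together, and under the stated ratio obeying the safety advice can count as non-adherence.

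The size depends on what the plan leaves open. On the scenario above, the goal is out of reach for such a participant over 8 or 12 weeks. Over 24 weeks it is attainable but demanding. With prescribed days counted from the quit date the ceiling disappears. The goal is therefore not shown to be impossible; as written, a miss could not be interpreted. The change is worth making before the 70% goal is used to judge feasibility. No view is taken here on when NRT should start or whether it may be used while smoking.

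**What to change.** - Reconcile sections 3.3.2, 6.1.1 (session table), 6.3.5 and 7.1 so that participants receive one consistent instruction on NRT use relative to smoking and the quit date. Which instruction is the clinical team's decision.
- In sections 6.1.3 and 6.4.1, define the adherence denominator as the days on which the reconciled instruction expects NRT use, with explicit start and end.
- State the window for the 70% goal (to Week 8, 12 or 24) and whether it is judged per person or as the arm mean.

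The cost is protocol wording and one redefined denominator. The daily medication log and the pharmacy refill review are already planned, so no new data are needed.
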